3.2 Exclusion Criteria

1. Impaired smell function as measured via standardized screening assessment
2. Unstable or significant medical condition in the past 12 months (recent heart attack or some other heart conditions, stroke, severe angina including high blood pressure)
3. Severe immune system disorders (uncontrolled Human Immunodeficiency virus infection; unstable multiple sclerosis symptoms), respiratory diseases (exacerbations of asthma or chronic obstructive pulmonary disorder, require oxygen, require oral prednisone), kidney (dialysis) or liver diseases (cirrhosis), or any medical disorder/medication that may affect participant safety or biomarker data
4. Women who are pregnant (verified by urine pregnancy test at any visit), trying to become pregnant, or nursing
5. Medical conditions associated with cognitive impairment or neurological dysfunction
6. Severe claustrophobia
7. Current depressive or anxiety disorder
8. Uncontrolled mental illness or substance abuse or inpatient treatment for these conditions in the past 6 months
9. Use of illicit drugs or prescription drugs for non-medical use daily/almost daily or weekly in the past 3 months per National Institute on Drug Abuse (NIDA) Quick Screen, not including use of marijuana
10. Any known risk from exposure to high-field strength magnetic fields (e.g., cardiac pacemakers), any irremovable metallic foreign objects in their body (e.g., braces), or a questionable history of metallic fragments which are likely to create artifact on the MRI scans
11. Known allergy to propylene glycol or vegetable glycerin
12. Other member of household currently participating in the study
13. History of a seizure disorder or had a seizure in the past 12 months
14. Currently taking or who have taken medications prescribed to prevent seizures (such as Carbamazepine or Phenobarbital). Using seizure medications for off-label use (indications other than treatment for seizures) will not be included as an exclusion, these will be assessed on a case-by-case basis

3.3 Early Withdrawal of Subjects

3.3.1 Criteria for removal from study

The Principal Investigator reserves the right to remove a participant from the study for any reason, based on their discretion.

Early Withdrawal Criteria Prior to Randomization: Participants who met any criteria below at Visit 2 will be considered for withdrawal prior to randomization:

1. Starting nicotine replacement therapy (e.g., patch, gum, lozenge, inhaler, nasal spray, Zyban, Chantix)
2. Use of other non-cigarette tobacco products in the past 7 days
3. Reporting a quit attempt in the past 7 days
4. Participant is not able to attend their Visit 2 Randomization visit within the study window.

General Withdrawal Criteria

1. Missing their study visit window: If a participant misses their study visit window, the participant will be considered for withdrawal from the study.
2. Not maintaining ECIG and cigarette use diary
3. New pregnancy: Participants who report a new pregnancy at any point during the study will be withdrawn.
4. Suicide attempt: If at any time during the study it is discovered that a participant has made a suicide attempt, they will be withdrawn from the study.
5. Cardiovascular disease (CVD) event requiring inpatient hospitalization: CVD typically includes MI (heart attack), PTCA (angioplasty/stenting), bypass surgery, stroke, peripheral vascular disease (arterial blockages in arms or legs leading to procedure or surgery). Less common CVD problems would be new cardiac arrhythmias (e.g., new atrial fibrillation) or new valvular disease (e.g., mitral or aortic regurgitation).
6. DVT/PE (deep vein thrombosis/pulmonary embolism, i.e., blood clots in the venous system) requiring inpatient hospitalization.
7. Psychiatric Inpatient Hospitalization: A participant will be withdrawn if he/she reports an inpatient hospitalization for psychiatric reasons at any time during participation in the study.
8. Participant choice: Participants may choose to remove themselves from the study by informing the research team in writing, by phone call or in person at any point during the study. If they choose to remove themselves from the study, they will not receive any further contact from the study center.
9. Adverse events related to ECIG use: Adverse events will be monitored at every study visit.
10. Worsening substance abuse in which the participant is behaving inappropriately at visits or demonstrates an inability to continue with the study.
11. Any inpatient hospitalization or debilitation in which participation in the study could be detrimental to the recovery process. This will be self-reported by the participant and will be reviewed by the site PI and medical professional to determine whether continued participation in the study is appropriate (this could include recovery from a major surgery, worsening of psychiatric symptoms, etc).
12. Any situation where participant is not able to use their ECIG for a period of more than 2 weeks (e.g. incarceration or other similar situation) unless they report not using the ECIG by choice.
13. Participant behavior: If a participant is behaving in an inappropriate or threatening manner, admits to lying about eligibility criteria, is participating in other smoking research studies that could affect the primary outcome measures, appears/admits to giving away/selling study products, consistently loses study products etc., then the PI can withdraw him/her from the study at the PI's discretion.

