3.3.2 Follow-up for withdrawn subjects

If participants are withdrawn from the study for any of the reasons noted above prior to randomization, they will be replaced until a total of 56 participants have been randomized to the study. Reasons for withdraw will be ascertained from subjects who withdraw from the study. In addition, among all participants who choose to withdraw, we will attempt to confirm their withdrawal and reason for withdrawal in writing (via mail or email).

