7.2.8 Daily Dairies for ECIG and Cigarette Use

Prior to randomization, participants will be asked to track the number of cigarettes smoked per day using a paper daily diary. They will also receive a daily REDCap survey link via text message (through Twilio) to enter their cigarette usage. During the 4-week ECIG conditioning period, participants will be required to record their ECIG use (in puffs per day) and the number of cigarettes smoked. A paper-based daily diary designed for data collection of each product type will be used. Participants will also continue reporting their use via REDCap survey links each evening. Research assistants will review the data entered by participants via the REDCap survey links at each visit. If participants did not complete the survey online, the researcher will ask the participant at each visit their ECIG and cigarette use. The diary will be used as a memory aid for the participant. (SEE ATTACHMENT: Cigarette Pack Daily Diary and E-cigarette and Cig Daily Diary)

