7.4.3 Method for Assigning Subject to Treatment Groups

Blocked randomization stratified across gender and matched for age will be accomplished with a 1:1:1:1 ratio of condition assignments with a goal of 56 randomized over a 7 month recruitment period. The randomization list will be stored in a password protected document that will only be accessed by unblinded study personnel.

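### Randomized participants can be withdrawn for a missed visit window or an unkept diary, with no Visit 4 scan sought, so the Aim 2 nicotine and Aim 3 flavor contrasts can be biased and lose numbers

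*Combined protocol and SAP*

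**What the plan says.** Section 3.3.1 has two lists. One is confined to the time before randomization and already has a rule for missing the Visit 2 window. The other, the General Withdrawal Criteria, is not limited in time. Its first item reads "If a participant misses their study visit window, the participant will be considered for withdrawal from the study". Its second is "Not maintaining ECIG and cigarette use diary", with no number of missed days and no statement of whether withdrawal is automatic. The section opens with a general discretion: "The Principal Investigator reserves the right to remove a participant from the study for any reason, based on their discretion". Item 12 covers being unable to use the ECIG for more than two weeks, but exempts participants "unless they report not using the ECIG by choice".

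On replacement, section 3.3.2 says: "If participants are withdrawn from the study for any of the reasons noted above prior to randomization, they will be replaced". For later withdrawals it provides only for recording the reason. Section 8.1 allows up to 75 enrolled to reach 56 randomized, so its margin covers losses before allocation only. Section 7.4.3 allocates "with a 1:1:1:1 ratio of condition assignments with a goal of 56 randomized", which is 14 per arm and 28 v 28 on each factor.

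Section 8.3 builds the outcome for change by subtracting the baseline image from the post-conditioning image. Sections 8.1 to 8.3 name no analysis population, missing-data method or sensitivity analysis.

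On use data, section 7.2.8 says: "If participants did not complete the survey online, the researcher will ask the participant at each visit their ECIG and cigarette use". It treats the paper diary as a memory aid. Section 7.4.4 uses the diary and the amount of product used to judge compliance.

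**The concern.** Items 1 and 2 concern attendance and record-keeping. They act after allocation, and both are tied to how engaged the participant is. Engagement could differ by arm: participants can perceive the flavor, and those given 0 mg lack nicotine reinforcement. It could also relate to the outcome, because more use means more pairings of odor and nicotine. If both hold, the people left at Visit 4 are no longer comparable across arms as randomized. A second scan that was never taken cannot be recovered at analysis.

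The exposed analyses are the two between-arm comparisons of change: 18 mg v 0 mg in Aim 2, and strawberry vanilla v tobacco within the 18 mg arms in Aim 3. Aim 1 uses baseline scans. The assigned-v-unassigned odor test in Aim 2 is made within one flavor group, so selection there affects whom the result describes, not an arm contrast.

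**Working it through.** **The plan's own figure.** Section 8.2 states 60% power for change between the nicotine and flavor groups. Take medium as d = 0.5 and alpha as 0.10 two-sided (both assumptions), with 28 per group. Power = Φ(d·√(n/2) − z) = Φ(0.5·√14 − 1.645) = Φ(0.226) = 0.589, or 0.58 with the noncentral t. This agrees with the stated 60% and assumes that all 56 are evaluable.

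**Loss of numbers.** No post-randomization loss rate is given, so 10-30% is assumed. Noncentral t, d = 0.5, alpha 0.10:

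| Loss | 28 v 28, two-sided | Aim 3, 14 v 14, two-sided | Aim 3, one-sided |
|---|---|---|---|
| 0% | 0.58 | 0.36 | 0.51 |
| 10% | 0.54 | 0.34 | 0.48 |
| 20% | 0.50 | 0.31 | 0.45 |
| 30% | 0.46 | 0.28 | 0.42 |

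Keeping 56 evaluable would need 56/(1 − loss) randomized: 63, 70 or 80.

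**Selection, 18 mg v 0 mg.** Illustrative model: in each group of 28 the k participants with the lowest latent adherence are removed, and adherence has correlation r with the change score (SD 1). The expected adherence of those kept, m(k), is minus the sum of the k lowest expected normal order statistics, divided by 28 − k. The six lowest for n = 28 are −2.014, −1.581, −1.327, −1.137, −0.981 and −0.846.

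- m(0) = 0
- m(2) = 3.595/26 = 0.138
- m(3) = 4.922/25 = 0.197
- m(6) = 7.886/22 = 0.358

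Shift in the 18−0 mg difference = r × [m(k at 18 mg) − m(k at 0 mg)]. Assumed ranges: 3-6 removed at 0 mg, 0-2 at 18 mg, r from 0.3 to 0.5.

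- Smallest: 0.3 × (0.138 − 0.197) = −0.018 SD, and 0.018/0.5 = 4%.
- Largest: 0.5 × (0 − 0.358) = −0.179 SD, and 0.179/0.5 = 36%.
- Equal removal: m is the same in both groups, so the shift is 0.

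The standard error of the difference at 28 v 28 is √(2/28) = 0.27 SD, so the shift is about 0.07 to 0.67 standard errors.

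**Does the direction hold?** Not necessarily. The model applies the same r in both groups. If adherence were unrelated to the outcome at 0 mg, removals there would cause no shift. Removing 0-2 at 18 mg would then move the difference upward by 0 to 0.5 × 0.138 = 0.07 SD.

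**Aim 3.** The bias model was not run for flavor within 18 mg, because the documents give no basis for assuming which flavor would lose more. Only the loss of power is quantified.

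**The case against.** A reader might infer that these criteria remove the least adherent users and so bias the arm comparisons. The documents do not support that. Withdrawal for a missed window is only considered, and the windows at Visits 3 and 4 are wide (±7 days). The diary item has no threshold. Staff help with barriers to compliance at Visit 3. Item 12 spares people who choose not to use the ECIG. The rules address diaries and attendance, not product use directly, and no document shows losses that differ by arm.

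A reader might also infer that section 7.2.8 makes the diary rule redundant. It does not: its fallback is for a missing online survey and uses the paper diary as an aid to memory, and section 7.4.4 relies on the diary for compliance.

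Nor is a late visit purely administrative. Visits 3 and 4 carry the adverse-event assessment and the COPD questionnaire. That stands, but it favors continued contact and does not explain the loss of the scan.

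Finally, this is a proof-of-concept study looking for trends, and the illustrated shift is smaller than one standard error. That limits the importance of the point. It does not remove it, because a study with 50-60% planned power for its between-subject comparisons has few participants to spare.

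**Conclusion.** The point holds as an exposure, not as a demonstrated bias. The plan allows adherence-related withdrawal after randomization on loosely defined grounds, with no Visit 4 scan sought and no replacement. It also has no stated analysis population or missing-data approach to protect the two between-arm contrasts of change.

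The size and direction of any bias are unknown. The range of −0.02 to −0.18 SD (4-36% of 0.5 SD) for 18 v 0 mg rests wholly on assumed removal counts, an assumed correlation common to both groups, and medium taken as 0.5 SD. The shift is nil under equal like-for-like removal and could change sign if the correlation differs by nicotine level. The loss of numbers is certain for anyone withdrawn before Visit 4: at an assumed 20% loss, power falls from 0.58 to 0.50 at 28 v 28, and from 0.36 to 0.31 (two-sided) for Aim 3.

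**What to change.** - State that, after randomization, a missed window or incomplete diary is recorded as a protocol deviation and does not by itself end data collection.
- Seek the Visit 4 scan from every randomized participant who is willing and safe to scan.
- Analyse all available scans in the arm assigned, report withdrawals by arm and reason, and add a per-protocol sensitivity analysis.
- Reconcile the diary criterion, item 12 and the use-reporting fallback in section 7.2.8. As written, someone who chooses not to use the product is exempt under item 12, while someone who uses it without keeping a diary may be withdrawn.

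The safety and participant-choice criteria are unchanged.

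Confining both items to the period before randomization would not work. The study ECIG is handed out only at the end of Visit 2, the earlier log covers cigarettes only, and the pre-randomization list already has a window rule.

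The cost is protocol wording and some effort to bring people back. The downside is that some scans will come from poorly adherent participants or fall outside the window, which may dilute the effect. The per-protocol analysis would help show how much, although it is itself open to the same selection.

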3.3.2 Follow-up for withdrawn subjects

If participants are withdrawn from the study for any of the reasons noted above prior to randomization, they will be replaced until a total of 56 participants have been randomized to the study. Reasons for withdraw will be ascertained from subjects who withdraw from the study. In addition, among all participants who choose to withdraw, we will attempt to confirm their withdrawal and reason for withdrawal in writing (via mail or email).

4.0 Recruitment Methods

4.1 Identification of subjects

All recruitment for this study will be routed through IRB STUDY00002213 which will also serve as the initial recruitment point of contact.

4.2 Recruitment process

4.2.1 How potential subjects will be recruited.

Interested volunteers calling the study center number will first complete the eligibility script and questions for IRB STUDY00002213 (screener 1). If a participant's responses match this study's specified inclusion criteria they will be forwarded to research staff for further phone screening (phone screener 2). Subjects that were unable to be reach by phone will have an email sent to them asking them to contact us via email or phone. A draft of the email will be uploaded to CATS.

Recruitment materials are included in IRB STUDY00002213.

4.2.2 Where potential subjects will be recruited.

Refer to IRB STUDY00002213 Call Routing Screener.

4.2.3 When potential subjects will be recruited.

Starting 2019 and running till 2024.

4.2.4 Describe the eligibility screening process and indicate whether the screening process will occur before or after obtaining informed consent. Screening begins when the investigator obtains information about or from a prospective participant in order to determine their eligibility. In some studies, these procedures may not take place unless HIPAA Authorization is obtained OR a waiver of HIPAA Authorization when applicable for the screening procedures is approved by the IRB. [For FDA regulated studies, consent for any screening activities would need to be obtained prior to screening unless specifically waived by the IRB.]

Verbal informed consent will be collected over the phone prior to screener 2. Potential eligible participants will be invited to take part in a remote visit where additional eligibility screening will occur. Written informed consent will be obtained before in-person randomization/MRI visits will begin.

5.0 Consent Process and Documentation

5.1 Consent Process:

Check all applicable boxes below:

- Informed consent will be sought and documented with a written consent form [*Complete Sections 5.2 and 5.6*]
- Implied or verbal consent will be obtained – subjects will not sign a consent form (waiver of written documentation of consent) [*Complete Sections 5.2, 5.3 and 5.6*]
- Informed consent will be sought but some of the elements of informed consent will be omitted or altered (e.g., deception). [*Complete section 5.2, 5.4 and 5.6*]

Informed consent will not be obtained – request to completely waive the informed consent requirement. [Complete Section 5.5]

5.2 Obtaining Informed Consent

5.2.1 Timing and Location of Consent

Screening portion: Subjects will have the screening portion of the study explained to them in detail over a phone call. They will have the opportunity to ask any questions and then will be asked to give their verbal consent to take part in the screening portion.

Randomization/MRI portion: When participants attend their remote screening visit, they will have the study explained to them in detail, and be given a long form consent form to look over before their in-person MRI visit. They will have the opportunity to ask questions at both visits and then will be asked to sign their consent form at the in-person visit. .

5.2.2 Coercion or Undue Influence during Consent

Once potential study volunteers are identified, they will be given information about the study and offered the opportunity to participate. The researchers obtaining consent will be instructed to clearly indicate that the participant's enrolling in the trial is purely voluntary and the researchers will not offer comments about whether they believe the participant should enroll in the study or not. Given the number of contacts and visits involved in the study protocol, the compensation provided to the participant is modest.

5.3 Waiver of Written Documentation of Consent

5.3.1 Indicate which of the following conditions applies to this research:

The research presents no more than minimal risk of harm to subjects and involves no procedures for which written consent is normally required outside of the research context.

OR

The only record linking the subject and the research would be the consent document and the principal risk would be potential harm resulting from a breach of confidentiality. Each subject will be asked whether the subject wants documentation linking the subject with the research, and the subject's wishes will govern. (*Note: This condition is not applicable for FDA-regulated research. If this category is chosen, include copies of a consent form and /or parental permission form for participants who want written documentation linking them to the research.*)

OR

If the subjects or legally authorized representatives are members of a distinct cultural group or community in which signing forms is not the norm, that the research presents no more than minimal risk of harm to subjects and provided there is an appropriate alternative mechanism for documenting that informed consent was obtained. (*Note: This condition is not applicable for FDA-regulated research.*)

Describe the alternative mechanism for documenting that informed consent was obtained:

Participants who are interested in the study will be asked to consent to allow the researcher to pre-screen them for the study over the phone and/or Zoom by asking all screening questions of all participants (eligible or ineligible). Participants will be asked if this information can be retained so that the study team will know reasons that participants are not eligible for the study.

5.3.2 Indicate what materials, if any, will be used to inform potential subjects about the research (e.g., a letter accompanying a questionnaire, verbal script, implied consent form, or summary explanation of the research)

Verbal script will be used as found “Phone Screener,” which is found in the supporting documents.

The written consent process will be documented in writing as follows::

- The current IRB approved long form written consent form will be used.
- The subject will sign the consent form during their in-person visit after all of the screening has taken place.
 - A copy of the consent form will be provided to the subject/representative. Whenever possible the consent form will be provided to the subject in advance of the consent discussion.

5.4 Informed consent will be sought but some of the elements of informed consent will be omitted or altered (e.g., deception).

5.4.1 Indicate the elements of informed consent to be omitted or altered

N/A

5.4.2 Indicate why the research could not practicably be carried out without the omission or alteration of consent elements

N/A

5.4.3 Describe why the research involves no more than minimal risk to subjects.

N/A

5.4.4 Describe why the alteration/omission will not adversely affect the rights and welfare of subjects.

N/A

5.4.5 If the research involves using identifiable private information or identifiable biospecimens, describe why the research could not be practicably be carried out without using such information or biospecimens in an identifiable format.

N/A

5.4.6 Debriefing

N/A

5.5 Informed consent will not be obtained – request to completely waive the informed consent requirement

5.5.1 Indicate why the research could not practicably be carried out without the waiver of consent
N/A

5.5.2 Describe why the research involves no more than minimal risk to subjects.
N/A

5.5.3 Describe why the alteration/omission will not adversely affect the rights and welfare of subjects.
N/A

5.5.4 If the research involves using identifiable private information or identifiable biospecimens, describe why the research could not be practicably be carried out without using such information or biospecimens in an identifiable format.
N/A

